1.1.3. Schedule of Events

Table C1: Schedule of Events for Part A

PROCEDURE/ASSESSMENTS ¹	Screening (D-28 to -1)	Surgery ² Day 0	POD1 ³	POD4 (±1 Day)	POD8 (±1 Day)	POD15 (±1 Day)	POD21	EOT/POD22 (+1 Day) ⁴	EOS/POD28 (±1 Day) ⁵
ICF, Demography, Medical History, FSH ⁶ (menopausal status)	X								
Determine Eligibility, Review Inclusion/Exclusion Criteria	X		X						
Ocular Symptoms Assessment ⁷	X		X	X (R) ¹⁶	X (R)	X (R)		X (R)	X (R)
ETDRS Visual Acuity	X		X	X (R)	X (R)	X (R)		X (R)	X (R)
Slit Lamp Biomicroscopy ⁸	X		X	X (R)	X (R)	X (R)		X (R)	X (R)
Indirect Ophthalmoscopy (dilated)	X								X (R)
IOP (Goldmann applanation tonometry) ⁹	X		X	X (R)	X (R)	X (R)		X (R)	X (R)
Blood Draw for Safety Lab Parameters (Part A only)			X					X (R)	X (R)
Blood Draw for Cortisol (pre-Randomization&POD22) (Part A only)			X					X (R)	
Randomization			X						
Dispense Study Drug			X						
Study Drug Dosing for 21 days (POD1 to POD21)			X ¹⁰	X	X	X	X		
Dispense Diary Card (with instructions for completion)			X	X	X	X			
Contact Subject ¹¹							X		
Collect Study Drug								X (R)	
Collect and Check Diary Cards for Accuracy and Compliance				X (R)	X (R)	X (R)		X (R)	
AEs ¹² and Concomitant Medications ¹⁵	X	X ¹³	X	X (R)	X (R)	X (R)	X ¹⁴	X (R)	X (R)

¹Ophthalmic assessments will be performed in the study eye only except at the Screening and EOS/POD28 visits or at subject early termination when the ophthalmic assessments will be performed on both eyes.

²Surgery must occur between one to 28 days after Screening, preferably in the morning. If, due to unexpected events, surgery is postponed and would occur > 28 days past the Screening visit, contact the Study Medical Monitor to determine which, if any, of the screening procedures should be repeated. Subjects will be determined to be a suitable candidate for surgery during a pre-surgery medical assessment, where the routine medication list prescribed by the cataract surgeon should be reviewed to rule out prohibited medications (Table 1).

³The POD1 visit must be scheduled between 18 to 34 hours following conclusion of surgery on Day 0. All assessments and blood draws done on POD1 are done prior to Randomization.

⁴POD22 is the End-of-Treatment (EOT) visit; subjects who discontinue study drug early (or early termination) should complete the POD22/EOT visit assessments (and indirect ophthalmoscopy) before or during their next scheduled visit.

⁵Subjects will have completed the study following the End-of-Study (EOS) visit on POD28.

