5.1.6.2. Missing data, rescue, last observation carried forward (LOCF)

LOCF	The last on study drug assessment is carried forward to impute a later missing value.
On study drug	Subjects are considered as being on study drug when they start their first dose until two days after their last dose of the study drug.

For efficacy analyses of POD1 to POD22 (Part A) and POD1 to POD15 (Part B), LOCF method will be used to impute all assessment values after the subjects that are rescued or early withdrawn and/or have stopped being on study drug to calculate mean, standard deviation, 95% confidence interval, median, Q1, Q3, minimum, and maximum for anterior chamber cell (ACC) count, ACC grade, ACF grade, pain grade, and Best Corrected Visual Acuity.

	Document Number: CLN.001.SAP	Version: 0
	Document Title: Clinical Study CPN-201 Statistical Analysis Plan	Page 16 of 35

Therefore, if a subject has an observed POD1 value for an efficacy endpoint, this subject should have observed or imputed values for the same endpoint through POD1 – POD22 for Part A or POD1-POD15 for Part B. Consequently, to avoid confusion, “POD22” will be used in place of “EOT” for Part A and “POD15” for Part B.

LOCF will not be used for “complete” subjects even if they have stopped study drug earlier than POD21 (Part A) and POD14 (Part B).

LOCF will not be used for safety analyses. For safety endpoints, the total number of subjects in the safety population and the summary statistics of all observed data will be calculated for each active dosing regimen and its matching vehicle placebo group for each visit.

Since the eye exams at Screening and EOS visits are evaluated as safety endpoints, the last non-missing observation from the study-eye at post-surgery PODs will not be carried forward to impute missing values at EOS visit for the Screening vs. EOS analyses.

To be clear, in any cases, EOS measurements will not be modified and Screening measurements will not be carried forward.

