5.1.9. Multiple Assessments at One Time Point

Where multiple assessments are recorded for a particular POD, e.g., ACC counts at the same visit or when two visits fall in the same POD window ([Table F](#)), the mean of the assessments will be calculated and used in any derivation of summary statistics. All observed data will be listed.

Note, for any efficacy endpoint:

If EOS falls in the same POD window ([Table F](#)) with another visit, the assessment obtained from that other visit, while the subject is still on study drug, will be used for the efficacy analyses.

If there are no other assessments in the same POD window ([Table F](#)) while the subject is still on study drug, e.g., within 2 days of the last dose of study drug as defined in 5.1.6.2, the EOS assessment will be used for efficacy analyses.

For any safety categorial endpoint, instead of taking the mean of all assessments within that POD window, the assessment obtained at the latest visit within that POD window will be used for that POD.

EOS assessments will not be modified in any case as mentioned in 5.1.6.2.

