5.3.2. Main analytical approach

The primary and secondary efficacy endpoints analyses will follow the General Consideration described in Section 5.1.

Efficacy analysis will be performed for the ITT population.

The primary efficacy endpoints and the secondary endpoints will be summarized in the same tables, figures, and listings.

Rescue and Early Withdrawal:

Rescue criteria: After randomization

- anterior chamber cells count >30 cells,
- an increase in anterior chamber cell count by > 15 cells from POD1/pre-dose baseline, or
- ≥ 2 grade of increase in ACF from POD1/pre-dose baseline.

For visits POD4 through EOS, the total number of subjects randomized, number of subjects who are still on study drug, and the number of subjects rescued for each reason and for subjects withdrawn early will be summarized in [Table 14.2.1](#) for each active dosing regimen and its matching vehicle placebo.

The denominator of each proportion is the number of subjects being randomized.

	Document Number: CLN.001.SAP	Version: 0
	Document Title: Clinical Study CPN-201 Statistical Analysis Plan	Page 20 of 35

Subjects' rescue and early withdrawn information together with reasons will be presented in [Listing 16.2.6.1](#).

Inflammation and Best Corrected Visual Acuity (BCVA) endpoints:

Both eyes at Screening and End of Study (EOS):

Although the tables for these data are numbered 14.2.xxx and listed with other efficacy endpoint tables, the analyses of parameters for eye exams at Screening and EOS visits, especially, those for the non-study-eye, are primarily considered as safety analyses and, therefore, they will be carried out for the safety population.

ACC count, ACC grade, pain grade, ACF grade, and ETDRS acuity (logMAR score) will be summarized descriptively for Screening and EOS visits for each active dosing regimen and its matching vehicle placebo. The summary statistics include total number of subjects in the safety population, mean, standard deviation, 95% confidence interval, median, Q1, Q3, minimum, and maximum of observed data. See [Tables 14.2.2.1.1-14.2.2.1.4](#), and [14.2.5.1](#).

The distribution of ACC, pain, and ACF grades for each treatment group will be described by the frequency within each grade for Screening and EOS visits. See the top part of [Tables 14.2.3.1 – 14.2.3.3](#).

Last non-missing observation from the other PODs will not be carried forward to impute missing values at EOS visit as discussed in Section 5.1.6.2.

Study eye only:

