The proportion of subjects with ACC count = 0, pain-free, or ACF grade = 0 without receiving rescue medication will be calculated for each active dosing regimen and its matching vehicle placebo for each visit during POD1 – POD22 (Part A) and POD1 – POD15 (Part B) in [Table 14.2.4](#) and [Figure 14.2.4](#). The denominator will be the total number of subjects randomized in each treatment group. LOCF will be used to impute missing values and all assessments after subjects stopped being on study drug.

All subjects' inflammation and pain information will be presented in [Listing 16.2.6.2](#) and best correct visual acuity information will be presented in [Listing 16.2.6.3](#).

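### In Table 14.2.4, a subject withdrawn onto other treatment for poor control can count as a later success on a sign last seen at zero, while a rescued subject cannot (minor, mainly Part B)

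*SAP*

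**What the plan says.** SAP 5.3.2, in the paragraph on Table 14.2.4 and Figure 14.2.4, sets the secondary responder endpoints: "The proportion of subjects with ACC count = 0, pain-free, or ACF grade = 0 without receiving rescue medication will be calculated". The denominator is everyone randomized to the arm. For values after dosing ends, the same paragraph states: "LOCF will be used to impute missing values and all assessments after subjects stopped being on study drug".

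SAP 5.1.6.2 does not separate the two ways of leaving: "LOCF method will be used to impute all assessment values after the subjects that are rescued or early withdrawn". Its definition is that the last on-drug "assessment is carried forward to impute a later missing value", and a subject stays on drug until two days after the last dose.

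Protocol 9.4.1 does separate them. Its three rescue criteria concern anterior chamber cells and flare; pain is not among them. Rescued subjects are called treatment failures. A subject who meets no criterion but is judged to need other treatment is 'Withdrawn', with a fixed reason entered in the eCRF. No sentence calls that subject a treatment failure.

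The reasons are available: SAP 5.3.2 says that subjects' "rescue and early withdrawn information together with reasons will be presented in" Listing 16.2.6.1.

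**The concern.** Both routes can describe the same event: study drug did not control the eye and another treatment was started. In Table 14.2.4 the label decides the outcome. Rescue already acts as a composite failure, so a subject rescued for flare also fails the pain-free endpoint. A subject withdrawn for pain with a quiet anterior chamber passes ACC = 0 and flare = 0 at every later visit, on values obtained before the other treatment began.

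Nothing in SAP 5.1.6.2, 5.3.1, 5.3.2 or the SAP Appendix sets such a subject to non-response for these endpoints. The SAP describes the study as a basis for choosing the Phase 3 regimen. With about 21 subjects per arm, one reclassified subject is visible in a proportion.

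**Working it through.** **Inputs.** 21 subjects per arm and 5% dropout (SAP 3); 132 subjects (SAP Appendix, Modifications); rescue criteria (Protocol 9.4.1, repeated in SAP 5.3.2); eligibility of more than 10 cells at POD1 (Protocol 4.2); the responder and LOCF rules above.

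**The plan's own figure.** 21 × (1 − 0.05) = 19.95, so about 20 per arm complete dosing through POD15, as stated. Expected early stops are 21 × 0.05 = 1.05 per arm, for all reasons.

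**The rule applied to one subject.** Take a Part B subject at the POD8 visit, still on drug, with ACC 12, pain 0 and flare 0, whom the investigator judges to need other treatment. These values are assumed for illustration.

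- ACC 12 does not exceed 30. The baseline was at least 11, so the rise is at most 1, not more than 15. Flare 0 cannot be a two-grade rise. No criterion is met, so the status is 'Withdrawn'.
- The POD8 examination is the last on-drug assessment and is carried to POD15.

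| Sign | POD8 value | POD15 by LOCF | If 'Withdrawn' | If 'Rescued' |
|---|---|---|---|---|
| ACC | 12 | 12 | fails | fails |
| Pain | 0 | 0 | success | fails |
| Flare | 0 | 0 | success | fails |

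The last column is not hypothetical. One sentence of Protocol 9.4.1 allows rescue medication at the investigator's discretion with no criterion met.

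A subject withdrawn at POD8 with pain 3, ACC 0 and flare 0 shows the mirror image: pain fails at POD15, and ACC and flare succeed.

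**Size per subject.** The shift is k/n for k such subjects in an arm of n.

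- n = 21: 1/21 = 4.8 percentage points.
- n = 22: 1/22 = 4.5 points, where 132/6 = 22 assumes an equal split over six arms.

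If each arm has zero or one such subject, in line with the expected 1.05 early stops, the active-minus-placebo difference moves by 0 to 4.8 points in either direction. A carried-forward success on placebo understates the drug effect; one on active overstates it.

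**Which Part.** The protocol's amendment rationale says that Amendment 1 followed review of about 41 Part A subjects who had completed POD15, out of about 42 planned. The rescued/withdrawn clarification came with that amendment, so the 'Withdrawn' process mainly governs Part B.

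**The case against.** The strongest reply is that the information is already reported elsewhere. Tables 14.2.3.1 to 14.2.3.3 give the proportion in each grade without LOCF over all randomized subjects, so a withdrawn subject adds nothing to grade 0 at later visits. The 'Resolved' proportions of SAP 5.3.4.1, in the same Table 14.2.4, fail every early discontinuation, and the Appendix applies its chi-square test to those. Rescue or early withdrawal is itself a listed secondary endpoint. All of this stands and lowers the severity. It does not repair the listed responder endpoints, and it leaves two opposite treatments of the same subject in one table.

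A second reply is that the endpoint refers to receiving rescue medication, not to holding the status 'Rescued'. Since Protocol 9.4.1 in one place allows rescue medication with no criterion met, some of these subjects may already fail. This also stands in part. But the same section elsewhere calls such a subject withdrawn and requires the rescue reason to be one of the criteria. The documents do not settle it.

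A reader might infer more: that even the sign that caused withdrawal could be carried forward as zero. That would need LOCF to run on the windowed values of SAP Table F and the withdrawal examination to be coded EOS. Then, if an earlier visit fell in the same window, "the assessment obtained from that other visit, while the subject is still on study drug, will be used for the efficacy analyses". If the examination were coded EOT, "the mean of the assessments will be calculated and used in any derivation of summary statistics", which is above zero. The LOCF definition in SAP 5.1.6.2, taken as written, carries the last on-drug assessment, so the failing sign stays a failure. The documents do not support the stronger inference.

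**Conclusion.** The concern holds as a minor one. Read literally, SAP 5.3.2 lets a subject withdrawn for poor control count as a later success on any sign whose last on-drug value was 0, where rescue would have made all three endpoints fail. It applies mainly to Part B.

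Each such subject is worth 4.8 points at 21 per arm, or 4.5 at 22 under an equal split. The documents give no count of such subjects, no arm split and no last values. A reader might infer a bias in favor of the drug, but no direction can be derived. The range of 0 to 4.8 points for the arm difference rests on the plan's own assumption of about one early stop per arm.

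The primary endpoints, ACC count and pain grade at POD15, do not use this responder rule, and all p-values are exploratory.

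**What to change.** In SAP 5.3.2, state that from rescue onward, or from withdrawal for the fixed Protocol 9.4.1 reason (need for other treatment of inflammation and pain) onward, a subject is a non-responder for ACC = 0, pain-free and flare = 0, whatever the last on-drug value. Say whether the visit of that decision is included. Leave LOCF unchanged for all other subjects, including those who stop drug for unresponsive IOP and keep attending under Protocol 9.1. Keep the present LOCF version as a sensitivity analysis, since judging each sign separately is also defensible.

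Identify the subjects from Listing 16.2.6.1. Check Part A subjects individually, because the fixed reason wording may not have been in use when they left.

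Two sets of passages must be reconciled:

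- the Protocol 9.4.1 sentences on who is rescued and who is withdrawn;
- the examination due at early termination. Footnote 4 of SAP Table C1 says "subjects who discontinue study drug early (or early termination) should complete the POD22/EOT visit assessments", and the Part B schedules (SAP Table C2, Protocol Table 2B) likewise call for EOT, while Protocol 6.2.7 and 9.4.1 call for EOS.

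The cost is one SAP paragraph and one derivation from reasons already collected, with slightly lower response rates where such subjects exist. The Appendix describes some comparisons in the past tense. If analysis has begun, the change is post hoc and should be documented and justified in the study report under SAP 5.1.11. The rule would still depend on the recorded reason: a subject withdrawn for an adverse event and then treated would keep the LOCF value.

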5.3.3. Sensitivity analysis

A subset of efficacy analyses will be examined for the per-protocol population as supportive analysis.

Since only first ACC count will be used to define the proportion of subject with ACC count = 0, analyses of using second ACC count and/or a combination of the two counts will be explored.

5.3.4. Supplementary Analyses

Exploratory hypothesis-generating analyses may be performed as necessary.

	Document Number: CLN.001.SAP	Version: 0
	Document Title: Clinical Study CPN-201 Statistical Analysis Plan	Page 22 of 35

5.3.4.1. Proportions of “Resolved”, “Unresolved”, and “Early discontinuation of study drug”

To understand the persistence of grade=0 for ACC (the first of two counts), ACF, and pain, proportions of “resolved”, “unresolved”, and “early discontinuation of study drug” will be calculated for each active dosing regimen and its matching vehicle placebo group at each POD in [Table 14.2.4](#) and [Figure 14.2.4](#).

A subject is defined as “Early discontinuation of study drug” at a POD when the subject is not on study drug at that POD. See Section 5.1.6.2 for the definition of on study drug.

A subject’s ACC (ACF, or pain) is defined as “Resolved” at a POD when the first of the two ACC counts (grade for ACF and pain) at that POD and all PODs beyond is equal to zero while the subject is still on study drug for all these PODs. Otherwise, the subject is “Unresolved”.

For example, if a subject’s first of two ACC counts equal to zero at POD8 but the first of two ACC counts >0 at POD15, this subject would be “Unresolved” at both POD8 and POD15.

If a subject’s first of two ACC counts >0 at POD22 (Part A) or at POD15 (Part B) this subject cannot be “Resolved” at any POD.

Apparently, a subject having an “Early discontinuation of study drug” can never be “Resolved” at any PODs. More precisely, this subject will be an “Early discontinuation of study drug” for all PODs beyond.

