1.4.2. Potential Benefits

Topical ocular administration of corticosteroids is a well-established therapy for the treatment of inflammation and pain after ocular surgery, with multiple marketed products currently available that utilize corticosteroids as the active ingredient such as dexamethasone (Maxidex®), prednisolone (PredForte®), loteprednol etabonate (Lotemax®, Inveltys™, and difluprednate (Durezol®). As summarized in the Product Inserts for Lotemax® and Durezol®, in clinical trials post ocular surgery, approximately 20-30% of subjects had clearing of anterior chamber cells and approximately 60-80% of subjects were pain free by Day 8 of treatment. Furthermore, approximately 40% of patients had clearing of anterior chamber cells and approximately 60% of patients were pain free after 15 days of treatment with Durezol®. In all clinical trials, corticosteroid therapies were dosed at a frequency of twice daily or more frequently. Thus, a more potent corticosteroid such as CP with a reduced dosing frequency may be advantageous over current therapies used to treat inflammation and pain following ocular surgery.

This is the first time that APP13007 will be administered to humans, therefore any potential direct benefit to subjects enrolled into this study is based on results of nonclinical pharmacology studies. However, given the potency of CP and known ocular use of corticosteroids, it is likely that subjects enrolled into this study and randomized to APP13007 may experience a reduction in inflammation and pain following cataract surgery.

It is known from clinical trials of products for the treatment of inflammation and pain after ocular surgery that a proportion of subjects randomized to placebo improve in the days following surgery (Lotemax® Product Insert 2018; Durezol® Product Insert 2017). Thus, there may be a marginal benefit to some of the subjects enrolled into the study that are randomized to placebo.

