4.2. Inclusion Criteria

To be eligible, a participant must meet the following criteria:

At the Screening Visit:

1. Provide signed and dated informed consent
2. Age ≥ 50 years at time of informed consent
3. If female, be of non-childbearing potential. Non-childbearing potential is defined as women who have been permanently sterilized or are postmenopausal. Postmenopausal is defined as amenorrhea for a minimum of 12 months (without an alternative medical cause) or an FSH greater than 40 IU/L. Note: FSH will not be required if subject reports amenorrhea for > 12 months. (Pregnant women or nursing mothers are excluded from the study.)
4. Expected to undergo unilateral uncomplicated cataract extraction via phacoemulsification and posterior chamber intraocular lens (PCIOL) implantation in one eye (designated the ‘Study Eye’)
5. In the Investigator’s opinion, have Early Treatment Diabetic Retinopathy Study (ETDRS) estimated potential of 0.7 (20/100) or better in study eye (best corrected visual acuity by pinhole method).
6. Willing and able to comply with study requirements and visit schedule; Able to either self-administer study medication or have someone available (e.g., spouse, caregiver, etc.) who can administer study medication according to the study schedule and instructions

At Postoperative Day (POD) 1/ Day of Randomization:

7. Have undergone unilateral cataract extraction via phacoemulsification and posterior chamber intraocular lens (PCIOL) implantation in the study eye without any additional procedures or complications that would, in the opinion of the Investigator, interfere with study procedures or confound study results
8. Have > 10 and ≤ 30 cells in the anterior chamber. (Note: Cell count should be taken twice at each visit and both counts need to meet eligibility.)
9. Have an IOP ≤ 30 mmHg.

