4.3. Exclusion Criteria

Participants will be excluded if they meet any of the following criteria:

1. Have a known sensitivity or allergy to clobetasol propionate, corticosteroids, or any of the study medication's components including benzalkonium chloride and soybean lecithin
2. Have an ACC > 0 or any evidence of intraocular inflammation (e.g., flare) in either eye as found during the slit lamp examination at the Screening visit
3. Have a score > 0 on the Ocular Pain Assessment in either eye at the Screening visit
4. Have an immunosuppressive or autoimmune disease that in the opinion of the Investigator could affect intraocular inflammation or the normal healing process of the eye
5. Have active or chronic/recurrent ocular or systemic disease that is uncontrolled and would likely affect wound healing and/or resolution of inflammation after cataract surgery.
6. Have suspected or known malignancy or received antineoplastic therapy within the 12 months prior to the Screening visit. Note: subjects with basal cell carcinoma will not be excluded unless the Investigator believes that the condition has the potential to interfere with study procedures or analysis of results.
7. Use of treatments for macular degeneration including Eylea® (aflibercept), Avastin® (bevacizumab), and Lucentis® (ranibizumab)
8. Use of systemic or topical anti-inflammatory agents, analgesics/pain relievers (including opioids, narcotics, NSAIDS, aspirin, acetaminophen and other pain medications) or immunomodulating agents systemically or in either eye (including Lifitegrast (Xiidra)) from the washout period until the End-of-Study (EOS) visit.
Note: Medication for anesthesia and pain control at surgery are allowed on the day of surgery only. (See Section 5.4.2.)
9. Use of any of the prohibited medications (see Section 5.4.2) within a time period prior to surgery that is less than the minimum 'washout' period noted in the table.
[NOTE: These medications may not be used after randomization through the EOS visit.]
10. Have an intraocular pressure (IOP) < 5 mmHg or > 22 mmHg in either eye at the Screening visit.
11. Have a history of documented repeated elevated IOP
12. History of herpes keratitis in the study eye
13. Have active corneal abrasions or ulcers in the study eye
14. Have active or a history of chronic or recurrent inflammatory eye disease (e.g., iritis, scleritis, uveitis, iridocyclitis, rubeosis iridis) in the study eye

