16	“LOCF will not be used for “complete” subjects even if they have stopped study drug earlier than POD21 (Part A) and POD14 (Part B).”	Removed from SAP.	The change reflects the intended purpose of the LOCF analysis.
21	For changes from baseline of ACC count, ACC grade, pain grade, ACF grade, and ETDRS acuity (logMAR score), statistical comparison between each active dosing regimen and its matching vehicle	
 1. The comparison was carried out for the means of the efficacy endpoints as well. 2. For efficacy endpoints, the Pearson-Chi-Square test was used to compare the proportions of 	New Exploratory analyses added.

	Document Number: CPN-201.SAP Appendix Document Title: Clinical Study CPN-201 Statistical Analysis Plan Follow-Up	Version: 1 Page: 4 of 5
--	---	--

	
placebo will be carried out for each visit during POD4 - POD22 (Part A) and POD4 – POD15 (Part B) using t-test and Mann-Whitney non-parametric tests.
	
“resolved” subjects (‘Sustained’ Grade = 0) between each active group and its matching placebo group at POD4 and sustained at all later visits.
 
3. IOP means and changes from baseline were compared between active treatment groups and their matching placebo groups.
	
21	
Sensitivity Analyses:
 
“A subset of efficacy analyses will be examined for the per-protocol population as supportive analysis.”
	
These analyses will not be conducted.
	
Only 5 out of 132 (3.8%) subjects were excluded from Per Protocol population because of protocol deviations. The differences from the LOCF analyses of efficacy endpoints will be negligible.

21	
Sensitivity Analyses:
 
“Since only first ACC count will be used to define the proportion of subject with ACC count = 0,
	
These analyses will not be conducted.
	
The analyses will use the first ACC count - this is comparable to real-world clinical practice. Because only 6 (4.5%) subjects had

	Document Number: CPN-201.SAP Appendix Document Title: Clinical Study CPN-201 Statistical Analysis Plan Follow-Up	Version: 1 Page 5 of 5
--	---	---

	
analyses of using second ACC count and/or a combination of the two counts will be explored.”
		
different ACC counts at a visit, the other analyses are redundant.

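### POD1 eligibility sets no pain or flare minimum, so subjects already at grade 0 on POD1 can count as pain-free, flare-free and 'Resolved', and no analysis of these proportions uses POD1 grade

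*SAP*

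**What the plan says.** **Entry.** The POD1 criteria in protocol 4.2 include "Have > 10 and ≤ 30 cells in the anterior chamber", which both counts must meet, and "Have an IOP ≤ 30 mmHg". No POD1 pain or flare grade is required. Pain and flare enter eligibility only at Screening, before surgery, when they must be absent. The exclusions in protocol 4.3 cover "Have a score > 0 on the Ocular Pain Assessment in either eye at the Screening visit" and "any evidence of intraocular inflammation (e.g., flare) in either eye".

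**Endpoints.** Pain grade at POD15 is one of the two primary efficacy endpoints (SAP 5.3.1). The secondary pain-free and flare = 0 proportions need only grade 0 and no rescue. For these, SAP 5.3.2 states: "The denominator will be the total number of subjects randomized in each treatment group". The supplementary category 'Resolved' (SAP 5.3.4.1) applies "when the first of the two ACC counts (grade for ACF and pain) at that POD and all PODs beyond is equal to zero", provided that the subject is still on study drug. None of these definitions asks for a POD1 grade above 0.

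**Comparison.** Section 2 of the SAP Appendix adds a Pearson chi-square test of the 'Resolved' proportions "between each active group and its matching placebo group at POD4 and sustained at all later visits". POD1 grades are recorded before randomization (protocol 6.2.2). Apart from plain change from baseline (protocol 10.3.2, SAP 5.3.2), no planned analysis uses POD1 pain or flare.

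**The concern.** The same word means different things in one table. For cells, every eligible subject had more than 10 on POD1, so a later sustained zero is clearance. For pain and flare, a sustained zero mixes two groups: subjects who had the sign on POD1 and lost it, and subjects who were at 0 on POD1 and stayed there. Table 14.2.4 shows all three signs together.

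At stake is how the pain and flare proportions are read. As rates of resolution they are too high, by an amount that depends on a share the documents do not give. The arm difference may also understate the effect in subjects who had something to treat. SAP section 1 says that the study is meant to select a regimen for Phase 3. Parts A and B are enrolled one after the other, so the same true effect could look larger in one Part than in the other merely because the POD1-zero share differs.

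**Working it through.** **1. The plan's own figure.** SAP section 3 enrols 21 per arm with 5% dropout: 21 × 0.95 = 19.95, about 20 completers. This reproduces. No power, effect size or POD1-zero rate is stated. Protocol 1.4.2 reports that with marketed products "approximately 60-80% of subjects were pain free by Day 8 of treatment", but that is a Day 8 rate and does not give the POD1 share.

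**2. Model.** Let *z* be the share at grade 0 on POD1, *s* the chance that they stay at 0, and *p* the 'Resolved' rate among subjects with grade 1 or more on POD1. The rate over all randomized is

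q = z·s + (1 − z)·p.

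If *s* is the same in both arms, the arm difference is (1 − z)(pA − pV), with A for active and V for vehicle.

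**3. Dilution.** Assumptions: s = 1, pA = 0.30, pV = 0.10 (a 20-point effect), z from 0.3 to 0.7.

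| z | active q | vehicle q | difference | POD1-zero share of 'Resolved' (z/q), active / vehicle |
|---|---|---|---|---|
| 0.3 | 0.3 + 0.7×0.3 = 0.51 | 0.3 + 0.7×0.1 = 0.37 | 14 points | 59% / 81% |
| 0.5 | 0.5 + 0.5×0.3 = 0.65 | 0.5 + 0.5×0.1 = 0.55 | 10 points | 77% / 91% |
| 0.7 | 0.7 + 0.3×0.3 = 0.79 | 0.7 + 0.3×0.1 = 0.73 | 6 points | 89% / 96% |

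A second assumed pair, 60% versus 20% with s = 1, behaves the same way. The 40-point difference becomes 32, 24 and 16 points at z = 0.2, 0.4 and 0.6. Exact power of the Pearson test at 21 per arm (two-sided 0.05, for illustration only) falls from 78% at z = 0 to 54%, 38% and 24%.

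**4. If staying at 0 differs by arm.** Take z = 0.5 and s = 0.90 on active versus 0.60 on vehicle (assumed), with the same *p*. Active is 0.45 + 0.15 = 0.60 and vehicle is 0.30 + 0.05 = 0.35. The difference is 25 points, larger than the 20 in the POD1-affected subset. Dilution is therefore conditional on equal *s*.

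**5. Chance imbalance.** With 21 per arm, the SD of the between-arm difference in POD1-zero share is √(2z(1 − z)/21): 15 points at z = 0.5, and 14 at 0.3 or 0.7. The counts differ by 4 or more with probability 17% at z = 0.2 and 27% at 0.4 or 0.6.

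For z = 0.5 in the table above, the ordinary SE of the difference is √((0.65×0.35 + 0.55×0.45)/21) = √(0.475/21) = 15.0 points. Its variance splits exactly into:

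- POD1 status: z(1 − z)[(1 − pA)² + (1 − pV)²]/21 = 0.25 × (0.49 + 0.81)/21 = 0.325/21, SD 12.4 points;
- the remainder: (1 − z)[pA(1 − pA) + pV(1 − pV)]/21 = 0.5 × (0.21 + 0.09)/21 = 0.150/21, SD 8.5 points.

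The 12.4 points lie inside the 15.0 and are not added to it. Stratifying by POD1 grade would remove roughly that component, leaving an SE near 8.5 points under these assumptions.

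**The case against.** The strongest reply is that the plan is sound as a randomized, descriptive comparison. Several parts of it stand.

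- *Bias.* A reader might infer that POD1-zero subjects bias the comparison, or that imbalance is an error on top of the usual one. Neither follows. Randomization keeps each active-versus-vehicle comparison unbiased, and the unadjusted SE already contains the imbalance (step 5).
- *'Never had the sign'.* A reader might infer that these subjects never had pain. The documents do not support that. Pain is rated at the time of the visit (protocol 7.2.1), POD1 falls 18 to 34 hours after surgery (6.2.2), and pain control is permitted on the day of surgery (5.4.2). Grade 0 on POD1 is a rating at one visit.
- *Prevention.* Staying at 0 may itself be a treatment effect, which the all-randomized rate captures and an affected-only subset would discard (step 4).
- *Other pain analyses.* Pain grade at POD15 and its change from POD1 are protocol primary analyses. 'Resolved' is supplementary, and all p-values are exploratory.
- *Visibility.* Table 14.2.4 starts at POD1, so the POD1-zero share will be seen. SAP 5.3.4.1 describes its aim as persistence of zero, and the Appendix glosses 'resolved' as sustained grade 0.

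These points limit the concern but do not remove it. A subject at 0 on POD1 can only stay or worsen on change from baseline, so that analysis has the same floor. Showing the POD1 row reveals an imbalance without adjusting for it. SAP 5.3.4 permits further analyses but commits to none.

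**Conclusion.** The concern holds in a limited form. Pain-free, flare = 0 and 'Resolved' for pain and flare include subjects at grade 0 on POD1 who stay at 0, and the Appendix test includes them without using POD1 grade. Absolute rates are therefore inflated as measures of resolution. If those subjects stay at 0 equally in both arms, an assumed 20-point effect shows as 14, 10 or 6 points at assumed shares of 30, 50 or 70%. At about 21 per arm, POD1 imbalance is an avoidable part of the standard error. Cell results are unaffected.

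The sizes rest on assumed values of *z*, *s* and *p*, because the documents give none. No separate figure was worked for flare.

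A reader might go further and infer that the trial cannot show whether APP13007 treats postoperative pain. The documents do not support that: the comparison is randomized, and pain grade and its change are analysed directly. What suffers is precision and the meaning of the proportions.

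**What to change.** Keep every all-randomized table. In SAP 5.3.2, SAP 5.3.4.1 and the Appendix comparison:

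1. For pain-free, flare = 0, and 'Resolved' pain and flare, give the active-minus-vehicle difference stratified by POD1 grade 0 versus 1 or more (Mantel-Haenszel, 95% CI).
2. Add supportive rows, with the number per arm, separately for subjects with POD1 grade 1 or more (resolution) and POD1 grade 0 (remaining at 0). The second row keeps any preventive effect in view.
3. Describe a sustained zero that starts on POD1 as 'grade 0 at POD1 and throughout'. Do not call it 'Resolved', and do not call it 'never present', since one visit's rating cannot show that.

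The cost is SAP wording and a few rows. The data are already collected before randomization and conduct does not change. The downside is small denominators in the POD1-affected rows: about 21 × (1 − z), or roughly 15, 10 or 6 per arm at z = 0.3, 0.5 or 0.7. Those rows should therefore stay supportive.
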